### Intervention period

September 1st 2008, to December 20th 2009.

### Background

Sarcopenia, the loss of muscle mass and strength during aging, is one of the main causes of the functional decline frequently observed among elderly people. Therefore, it is considered very important to establish therapies that prevent or delay sarcopenia.

Regular resistance training is an effective way to increase muscle mass and strength in elderly people. It has also been suggested that strategies such as increased protein intake and/or supplementation with essential amino acids, in particular leucine, could maximize gains in muscle mass or strength during a resistance exercise program. In that regard, research has been directed towards whey proteins due to their high quality. Studies in young people indicate that whey protein ingestion directly after exercise stimulates muscle protein synthesis more than other protein sources.

The beneficial effect of whey protein is thought to occur primarily due to their very high concentration of essential amino acids, particularly leucine (up to 14%). In general, studies suggest that ingestion of essential amino acids is an effective way to stimulate muscle protein synthesis in

both young and elderly individuals, whereas non-essential amino acids appear to have no detectable effect. Therefore, it seems reasonable to assume that ingestion of whey protein supplements, with their high amount of essential amino acids, would result in greater gains in muscle mass after a period of resistance exercise in elderly people than, for example, isocaloric carbohydrate supplements. However, studies on the effect of whey protein on muscle mass and strength gain in elderly people are few and it is unclear whether findings from short time experiments on muscle protein synthesis can be extrapolated to a long-term increase in muscle mass or strength.

## Hypothesis

Sarcopenic participants receiving whey protein supplementation or milk during resistance training will experience greater gains in lean body mass, strength, and physical function compared to participants receiving isocaloric carbohydrate.

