## Subjects

It is planned to recruit 250 participants, older than 65 years, and to keep the proportion of men and women similar. Volunteers will be recruited by advertisement posters in Hrafnista in Hafnarfjörður, a home for the elderly in the capital area of Iceland, and other areas in the capital area of Iceland. If cardiovascular disease symptoms will be detected during screening, participants will be encouraged to contact their physician for medical clearance.

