## Exclusion criteria

Exclusion criteria are age younger than 65 years, low cognitive function (Mini-Mental State Examination (MMSE) <19 points), evidence of uncontrolled coronary heart disease, major orthopedic disease, and pharmacological interventions with exogenous testosterone or other drugs known to influence muscle mass. Furthermore, all participants have to be free of any musculoskeletal disorders or other disorders that could affect their ability to complete their training and testing.

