## Dietary intervention

Participants will be randomly assigned to one of three different supplement drinks, produced and developed by Mjólkursamsalan (Icelandic dairy producer), which will be packaged into 250 mL brick-style aseptic cartons. The drinks will be based on a sweet whey concentrate (lean cream), low-fat milk protein concentrate, and carbohydrates (placebo).

The supplement drinks will be provided in identical containers and flavoured to mask the contents. All of the drinks will be isocaloric and have the same amount of fat. The whey protein drink and low-

fat milk drink will contain the same amount of protein and carbohydrates, and will only differ from the carbohydrate drink in their protein and carbohydrate contents. Participants will ingest 250 mL of the supplement immediately after each workout, under supervision of study staff, while maintaining their habitual daily diet.

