## **Randomization and masking**

Treatment assignment will be randomized and double blinded. Participants will be randomly allocated to treatment groups following a stratified randomization procedure based on a computer-generated list of random numbers. Randomization will be stratified by gender to make the proportion of men and women in each group equal. The supplement drinks will be provided in identical brick-style cartons and each of the two supplements will have a specific 3-digit-labelling. Investigators and other staff will be kept blind to supplement assignment by the producer of the supplement until the end of the intervention. Furthermore, the supplement drinks will be flavoured to mask the contents.

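### The hypothesis is about sarcopenic participants, but the entry criteria select older volunteers without regard to muscle mass, strength or function

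*Protocol*

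**What the plan says.** The Hypothesis section names its population in its first words: "Sarcopenic participants receiving whey protein supplementation or milk during resistance training will experience greater gains in lean body mass, strength, and physical function". The comparator is the isocaloric carbohydrate group.

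The Subjects section describes who will be enrolled: "It is planned to recruit 250 participants, older than 65 years, and to keep the proportion of men and women similar". On the route of entry it says: "Volunteers will be recruited by advertisement posters in Hrafnista", a home for the elderly, and adds other parts of the capital area.

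The exclusion list opens: "Exclusion criteria are age younger than 65 years, low cognitive function (Mini-Mental State Examination (MMSE) <19 points". It goes on to uncontrolled coronary heart disease, major orthopaedic disease and drugs that affect muscle mass, and closes with a general condition: "all participants have to be free of any musculoskeletal disorders or other disorders that could affect their ability to complete their training and testing".

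The term itself appears in the Background only as a general description: "Sarcopenia, the loss of muscle mass and strength during aging, is one of the main causes of the functional decline". No cut-off or operational definition follows there or anywhere else in the protocol.

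**The concern.** A hypothesis states for whom the effect is claimed, and the entry criteria determine for whom it is estimated. Here the two differ. Nothing at entry requires a participant to have low muscle mass, low strength or poor function, so the randomised sample is a mixture of sarcopenic and non-sarcopenic older people in unknown proportion.

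What is at stake is the attribution of the result. If the conclusion is drawn in the terms of the hypothesis, a positive finding would be credited to sarcopenic people, and a null finding counted against the supplements in them, although the trial neither selected nor identified that population. The effect in sarcopenic people may or may not equal the average effect in the sample, and the planned comparison does not separate the two.

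**Working it through.** **Step 1: the sections side by side.**

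| Protocol section | Population it refers to | Sarcopenia criterion? |
|---|---|---|
| Background | Sarcopenia described in general terms; the rationale for the trial speaks of elderly people | No cut-off |
| Hypothesis | Sarcopenic participants | Named, not defined |
| Subjects | 250 volunteers over 65 | None |
| Exclusion criteria | Age, MMSE, coronary and orthopaedic disease, drugs, disorders that limit training or testing | None |
| Randomization and masking | Stratified by gender only | None |
| Statistical analyses | Groups compared by general linear models | None |
| Power calculations | Participants per group | None |

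DXA body composition, grip strength, quadriceps strength, timed up and go and six-minute walk are all measured, but the protocol uses none of them to classify participants. The hypothesis is the only section that restricts the population to sarcopenic people.

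**Step 2: the protocol's own sample size.** Inputs from Power calculations: difference 1 kg, SD 2 kg, power 0.8, P = 0.05. Sidedness is not stated; a two-sided test reproduces the figure.

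n per group = 2 × (1.960 + 0.842)² × 2² / 1² = 2 × 7.85 × 4 = 62.8, rounded up to 63. Power at 63 per group is 0.801. A two-sample t calculation gives 64, and a one-sided test gives 50, which does not match. The stated 63 is therefore correct and is not in dispute.

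**Step 3: how much of the sample would have to be sarcopenic.** The number of arms comes from the Dietary intervention section: "Participants will be randomly assigned to one of three different supplement drinks". The allocation ratio is not stated, so equal arms are assumed. To have 63 sarcopenic people in each arm:

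3 × 63 = 189, and 189 / 250 = 75.6% of those enrolled.

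**Step 4: power among sarcopenic participants alone, by assumed share.** For a share p, the number per arm is m = 250p / 3, and power = Φ(√(m/2) × 1/2 − 1.960). Assumptions: equal arms, no dropout, and the same 1 kg and SD of 2 kg in this subset.

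| Assumed share p | m per arm | Power |
|---|---|---|
| 10% | 8.3 | 0.17 |
| 20% | 16.7 | 0.30 |
| 30% | 25.0 | 0.42 |
| 50% | 41.7 | 0.63 |
| 75.6% | 63.0 | 0.80 |
| 100% | 83.3 | 0.90 |

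The protocol gives no figure for p, so the table shows only how far the answer depends on an unknown. It describes a subset comparison that the protocol does not plan, and it is no criticism of the planned comparison.

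**The case against.** The strongest reply is that the hypothesis uses the word loosely. The Background defines sarcopenia as a process of ageing, without a threshold, and then builds its rationale on elderly people in general. On that reading everyone over 65 is sarcopenic to some degree, and a single adjective is out of line. This has some force, because it shows that the rest of the protocol is coherent. It does not remove the mismatch: the same Background section says that therapies are needed to prevent sarcopenia or postpone it, which presupposes older people who do not yet have it. If all volunteers over 65 are meant, the hypothesis should say so.

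A second reply is that the SAP, which is not at hand, may define a sarcopenic subset. That stands as far as the analysis goes, so the absence of a cut-off or an interaction model from the protocol is not held against it. Entry criteria and the hypothesis belong in the protocol, however, and an SAP cannot change who was randomised.

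Three stronger readings are tempting, and the protocol does not support them:

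- *Recruitment selects against sarcopenia.* A reader might infer this from the requirement to be able to complete the training. But the exclusions do not name low muscle mass or weakness, training loads are set relative to each person's own 1-RM, the timed up and go may be done with the usual walking aids, and one recruitment site is a home for the elderly. The net direction of selection is unknown.
- *Sarcopenic participants would be few and the trial underpowered for them.* That needs a low share, and the protocol supplies none. It also faults the trial for a test it does not propose.
- *The trial cannot answer its question at all.* The randomised comparison remains internally valid. What fails is the description of the people to whom it applies.

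**Conclusion.** The point holds as a mismatch between the stated hypothesis and the selected population. As written, the trial estimates supplement effects in volunteers over 65, and the result could not be attributed to sarcopenic participants. This rests on the protocol's text alone and needs no assumption about prevalence.

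Only the numerical size depends on assumptions. Across assumed shares of 10% to 100%, power in the sarcopenic subset runs from 0.17 to 0.90, with 80% kept only at about 76% or more. Nothing in the protocol shows where in that range the trial would fall.

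Severity is moderate. The hypothesis is wrong as worded, which affects what may be concluded, but the randomisation, the 63 per group and the main comparison are untouched.

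**What to change.** Reword the hypothesis, and any conclusion drawn from it, so that the population is adults over 65 not selected for sarcopenia. That agrees with the elderly people of the Background rationale and with the Subjects and Exclusion criteria sections.

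Optionally, report the share of participants with low muscle mass or low strength from the baseline DXA and grip measurements already planned, by one named cut-off. This, and any look at whether the supplement effect varies with baseline lean mass, should be labelled descriptive or exploratory.

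The cost is a change of wording and, if the option is taken, one descriptive table from data already collected. The downside is a less specific claim. Recruitment, sample size and the main comparison do not change. Keeping the present wording would instead need an operational definition applied at entry. On the protocol's own 63 per group, that means screening about 189/p volunteers: 189 / 0.5 = 378 at a 50% share, or 189 / 0.2 = 945 at 20%.

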## Study design

Subjects will participate in a 12-week randomized and controlled resistance exercise intervention program, designed to increase strength and muscle mass of all major muscle groups. All data will be obtained at baseline and again at the end of the study.

## Subjects

It is planned to recruit 250 participants, older than 65 years, and to keep the proportion of men and women similar. Volunteers will be recruited by advertisement posters in Hrafnista in Hafnarfjörður, a home for the elderly in the capital area of Iceland, and other areas in the capital area of Iceland. If cardiovascular disease symptoms will be detected during screening, participants will be encouraged to contact their physician for medical clearance.

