## **Resistance exercise**

Subjects will exercise for three non-consecutive days per week for 12 weeks in groups of 20-30 individuals. Before the intervention starts, 1-repetition maximum (1-RM) will be assessed using weight machines and by progressively increasing the weight lifted until the participant fails to lift the weight. The first week will be used to teach correct exercise techniques at lower loads (60% of 1-repetition maximum (1-RM)). Thereafter, resistance training will involve 3 sets, where each exercise will be repeated 6-8 times, at 75-80% of 1-RM. The training load will be systematically increased by 5-10% each week in order to keep the number of repetitions per set between six and eight.

Ten different exercises will be performed in weight machines during each training session; seated leg extension, seated leg curl, seated leg press, seated chest fly, seated row, seated pull-down, seated biceps curl, seated triceps curl, seated lower back extension, and seated abdominal curl. Each exercise session will start with a moderate, 10- to 15-minute aerobic warm-up on a treadmill or a stationary exercise bicycle, after which resistance training with weight machines will be performed.

Stretching exercises will be performed at the end of each session. Each session will be supervised by study staff, an athletic trainer, and occasionally a physiotherapist.

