### **Blood pressure**

Baseline fasting blood pressure will be measured in the morning with a Medisana upper arm blood pressure monitor (Medisana AG, Neuss, Germany) after a 12 hour fasting. All blood pressure measurements will be performed by qualified health care staff while the participant sits still and relaxed in sitting position with the upper right arm exposed. During the measurements the subject will be asked not to engage in conversation and the arm of the subject will be allowed to rest on a desk so that the antecubital fossa will be at approximately the same level as the heart. Two readings will be taken at intervals of 2 minutes and the average of those readings will represent the patient's blood pressure. The third reading will be performed when the difference between the first two readings is greater than 10 mmHg. Participants will be asked not to take any antihypertensive drugs for 12 hours prior to the measurements.

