### **Demographics and other relevant variables**

All participants will be asked to answer questions regarding their level of education, leisure-time physical activity, professional activity and spouse's profession (before retirement), as well as alcohol and smoking habits. Smoking and alcohol consumption will be categorized as never, former, or current. Information about health problems and medications will also be collected.

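### Physician clearance for volunteers with cardiovascular symptoms is advised but not required before 1-RM testing and training

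*Protocol*

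**What the plan says.** The Subjects section deals with cardiovascular symptoms detected at screening in one sentence. The action it sets is that "participants will be encouraged to contact their physician for medical clearance".

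The Exclusion criteria section is mandatory. It excludes "evidence of uncontrolled coronary heart disease" and also requires participants to be free of "other disorders that could affect their ability to complete their training and testing".

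Other sections give staff relevant information. Under Demographics and other relevant variables, "Information about health problems and medications will also be collected". Under Blood pressure, "All blood pressure measurements will be performed by qualified health care staff". Study design makes these baseline data: "All data will be obtained at baseline and again at the end of the study".

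On physical effort, the Resistance exercise section states: "Before the intervention starts, 1-repetition maximum (1-RM) will be assessed using weight machines". The method is "progressively increasing the weight lifted until the participant fails to lift the weight". Week 1 of training is then at 60% of 1-RM, and later weeks are at 75-80%.

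**The concern.** The protocol recognises that a symptomatic volunteer may need a medical opinion and names clearance as the purpose of seeing a physician. It then leaves that step to the volunteer. It does not say that clearance must be in hand before randomisation, 1-RM testing or training, or what happens if clearance is refused or never sought.

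What is at stake is the safety of people over 65, some of them recruited through a home for the elderly. A symptomatic volunteer who is not excluded could lift to failure with no physician having considered whether that is wise. Bias, power and the group comparison are not in question.

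**Working it through.** The protocol has no figure to reproduce here, so the check is whether any section turns the advice into a requirement.

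| Protocol section | What it provides | Does it require clearance? |
|---|---|---|
| Subjects | Encouragement to see a physician when symptoms are detected | No |
| Exclusion criteria | Mandatory exclusion for uncontrolled coronary heart disease and for disorders affecting training or testing | No. It names no assessor and does not make symptoms as such an exclusion |
| Ethical considerations | Ethics and data-protection applications, Helsinki guidelines, written consent before data collection | No |
| Blood pressure | Baseline readings by qualified staff | No. No action is tied to the result |
| Demographics and other relevant variables | Health problems and medications recorded | No. No action is tied to the result |
| Resistance exercise | 1-RM test to failure, lighter week 1, supervised sessions | No |

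Taken in the order a volunteer would meet them:

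1. Symptoms are found at screening. Staff apply the exclusion criteria, and anyone judged to meet one leaves. The Subjects sentence presupposes that some symptomatic people remain; otherwise its reference to clearance would have little purpose for entry.
2. Those who remain are advised to see a physician. Whether they do so or not, no section holds them back.
3. They take the 1-RM test, which comes before the intervention and raises the weight until a lift fails. The lighter first week at 60% of 1-RM comes afterwards, so it cannot protect against risk in the test.
4. From week 2 they train at 75-80% of 1-RM. Sessions are supervised by study personnel and an athletic trainer, with a physiotherapist at times. No physician is listed.

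The affected group must therefore meet three conditions together: symptoms detected at screening, no exclusion criterion judged to apply, and no clearance obtained. The protocol gives no rate for any of the three, so the size of the group cannot be calculated.

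**The case against.** The strongest reply is that the main barrier is already compulsory. A cardiovascular symptom that raises real doubt about lifting to failure fits naturally under the clause on disorders affecting training and testing. On this view the plan is graded: exclude the unfit and refer the rest, with the referral as an extra layer. This stands in part. It narrows the group considerably, and staff could in practice withhold entry. It does not close the gap, because nothing obliges staff to withhold entry for symptoms as such. Deciding whether coronary disease is uncontrolled, or whether a disorder limits training, may itself need the medical opinion that is left voluntary.

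A second reply points to ethics approval, the Helsinki guidelines and written consent. These are general protections and contain no clearance step. The consent form was not available for this review and might carry such an instruction. Even so, the sentence in the Subjects section would remain weak as written.

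A third reply is that the protocol does not define cardiovascular symptoms, so a firm bar would rest on a loose trigger and might be applied unevenly. That is fair, but the loose trigger is already in the protocol. Making the existing step binding does not create it.

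Finally, no number affected and no size of harm can be shown. That is correct, and it limits how strongly the point can be put.

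**Conclusion.** The concern holds, within narrow limits. A site following the protocol exactly may let a symptomatic volunteer who is not excluded do 1-RM testing to failure and then train at 75-80% of 1-RM without a physician's clearance. Eligibility and safety clearance belong in the protocol, so a separate statistical analysis plan would not be expected to supply them.

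The conclusion rests on the wording of the sections compared above and assumes that the consent material imposes no stricter rule. It makes no claim about how many people are affected or how likely harm is, and the validity of the group comparison is untouched. The point should be fixed because the safeguard is already named and making it binding is cheap.

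**What to change.** Replace the last sentence of the Subjects section with a rule to this effect: a volunteer found at screening to have cardiovascular symptoms is randomised and undergoes 1-RM testing only after written physician clearance is on file, and is otherwise not enrolled. The Exclusion criteria section stays as it is. A short list of qualifying symptoms and a named role to make the decision would help staff apply the rule evenly.

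The core change is one sentence and one line on the screening form, using a physician contact the protocol already foresees. The downside is that some volunteers will be delayed or not enrolled. Their number cannot be estimated, because the symptoms are undefined and no rate is given.

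The recruitment margin shows what room there is:

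- Required (Power calculations): 3 × 63 = 189.
- Planned (Subjects): 250.
- Margin: 250 − 189 = 61, or 61/250 = 24.4% of planned recruitment.

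If *k* volunteers are not enrolled and not replaced, the margin is 61 − *k*, and it must also absorb dropout. If recruitment continues until 250 are enrolled, the margin is unchanged. This arithmetic bears only on the cost of the change, not on whether clearance should be required.
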